7.3 LOST TO FOLLOW-UP

A participant will be considered lost to follow-up if she fails to return for scheduled visits and study staff are unable to contact the participant after at least 3 attempts.

The following actions must be taken if a participant fails to return for a required study visit:

The site will attempt to contact the participant, reschedule the missed visit, counsel the participant on the importance of maintaining the assigned visit schedule and ascertain if the participant wishes to and/or should continue in the study.

Before a participant is deemed lost to follow-up, the investigator or designee will make every effort to regain contact with the participant (where possible, 3 telephone calls). These contact attempts will be documented in the participant's study file.

Should the participant continue to be unreachable, she will be considered to have withdrawn from the study with a primary reason of lost to follow-up.

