4.4 END-OF-STUDY DEFINITION

A participant is considered to have completed the study if she has completed Time 1 (baseline), Time 2 (6 months) and Time 3 (12 months) data collection.

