To strengthen retention, our intervention sessions will be interactive, with culturally-tailored content developed to engage and sustain participants' interest (*Su Corazón, Su Vida* curriculum and coping skill training). Women who miss a learning session will be offered an opportunity to review the weekly class content over the phone, and will be reminded when the next class will be held. We will provide women with handouts including tips, a list of resources, recipes, and illustrations in Spanish on how to improve their nutrition, physical activity, and sleep. We will ask participants for phone numbers of family members and permission to call them if we cannot contact them. We will be flexible in scheduling enrollment and data collection appointments and send thank you cards. We will remind participants of their data collection visits one week before and confirm the day before the appointment. Participants in both groups will receive \$35 after the baseline visit, \$40 after the 6-month visit, and \$45 after the 12-month data collection. These approaches have been successful in prior studies with Latinas, with <20% attrition [43]. We will make every effort to keep our attrition lower than 20%; if attrition exceeds 20%, we will contact the participants to ask why they stopped coming and develop strategies to assist them to continue in the study if they wish. We will also meet with our Community Advisory Board to develop and implement strategies to improve retention.

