7.2 PARTICIPANT DISCONTINUATION/WITHDRAWAL FROM THE STUDY

Participants are free to withdraw from participation in the study at any time upon request.

An investigator may discontinue a participant from the study for lost-to-follow up and unable to contact subject.

The reason for participant discontinuation or withdrawal from the study will be recorded. Participants who sign the informed consent form and are randomized but do not receive the study intervention may be replaced. Subjects who sign the informed consent form, and are randomized and receive the study intervention, and subsequently withdraw, or are discontinued from the study will not be replaced.

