9.3 POPULATIONS FOR ANALYSES

Means, standard deviations, minimums, medians, and maximums will be determined for each continuous variable; frequencies and percentages will be tabulated for each categorical variable. Preliminary analyses will be performed to determine whether, despite randomization, the intervention and control groups were unbalanced on age, education, income, or other participant characteristics. Any variable with an imbalance between the groups at baseline will be examined to determine whether it is related to any of the outcome variables. If significant relationships are identified, the variable will be included as a covariate in the models for the affected outcome(s) as a potential confounder. An intent-to-treat analysis will be used in which all subjects are included in the analysis and analyzed according to their initial randomized assignment.

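### Section 7.3 classes a woman still unreachable after a missed visit as withdrawn and provides for no Time 3 attempt, though month 12 is the only scheduled follow-up for six of eight biologic primary outcomes

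*Combined protocol and SAP*

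**What the plan says.** Section 7.3 has three parts.

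- **Definition:** "A participant will be considered lost to follow-up if she fails to return for scheduled visits and study staff are unable to contact the participant", with a minimum of three attempts. Visits are in the plural.
- **Trigger:** "The following actions must be taken if a participant fails to return for a required study visit". Here one visit is enough. The actions are to contact her, reschedule, counsel her, and find out whether she wishes to continue. Every effort is to be made to regain contact, by three telephone calls where possible.
- **Consequence:** "Should the participant continue to be unreachable, she will be considered to have withdrawn from the study", with loss to follow-up recorded as the main reason.

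Section 7.2 treats withdrawal by the participant as something she requests. It then adds a discretionary ground: "An investigator may discontinue a participant from the study for lost-to-follow up and unable to contact subject".

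Section 5.5 sets up a second route to the participant: "We will ask participants for phone numbers of family members and permission to call them if we cannot contact them". It also says that if attrition passes 20%, staff will contact women who stopped coming and help those who wish to continue.

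Section 4.1 has two follow-up visits, Time 2 (6 months) and Time 3 (12 months). The schedules in 1.3 and 8.1 place glucose, the lipid profile and pulse wave velocity at 0 and 12 months only. Section 3 lists enrollment and retention rates among the primary outcomes.

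**The concern.** A missed visit and a withdrawal are different events. The first costs the data of one visit; the second ends follow-up. Section 7.3 moves a woman from the first to the second because of silence, not a decision of hers. It names no intermediate status, no route back, and no attempt at the next visit.

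With only two follow-up visits, this matters most at Time 2. For six primary outcomes nothing was due at that visit, so missing it costs nothing on those measures. The loss comes from the classification, if a site takes withdrawn to mean that no month-12 visit need be arranged. Retention is also affected, because a woman recorded as lost at month 6 counts as lost whether or not she could have been found at month 12.

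**Working it through.** **1. Count the outcomes.** Section 3 lists eight biologic primary outcomes: systolic and diastolic blood pressure, pulse wave velocity, total cholesterol, HDL, LDL, triglycerides and fasting glucose. Those scheduled at 0 and 12 months only are pulse wave velocity (1) + glucose (1) + lipids (4) = 6 of 8. The two schedules differ on blood pressure at month 6: 1.3 marks it and 8.1 does not. Section 9.4.6 analyses blood pressure at Time 2, which supports 1.3. The count of six is the same in both tables.

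**2. Follow a woman who misses Time 2 and stays unreachable.**

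| Step | Source | Result |
|---|---|---|
| Misses one required visit | 7.3, trigger | Contact steps start |
| Not reached after at least three attempts | 7.3, consequence | Considered withdrawn, reason lost to follow-up |
| Same facts | 7.3, definition | Lost only if *visits* (plural) were missed |
| Same facts | 7.2 | Investigator *may* discontinue her |
| Month 12 | No section | No attempt provided for |

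The three rules differ. On the plural reading she could not be lost until Time 3 was also missed, since there are only two follow-up visits. On the singular trigger she is withdrawn at month 6. Under 7.2 it is the investigator's choice.

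**3. Effect on the analysis.** Section 9.4.1 tests change with a t-test or Mann-Whitney test and states no missing-data method. Without a Time 3 value she has no change score for the six outcomes. Section 2.3.1 mentions general linear mixed models instead, but with only a baseline value she would add almost nothing to an estimate of change there either.

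**4. Size, as an illustration.** The documents give neither the share of losses that are women unreachable at Time 2 nor the share of those reachable at month 12. Take the 20% figure in 5.5: 0.20 × 80 = 16 women lost. Both shares below are assumptions.

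| Share of the 16 unreachable at Time 2 | Women | 25% reachable at month 12 | 50% reachable |
|---|---|---|---|
| One quarter | 4 | 1 | 2 |
| One half | 8 | 2 | 4 |
| Three quarters | 12 | 3 | 6 |

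In the middle row, 2/80 = 2.5 and 4/80 = 5 percentage points of retention.

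**5. What that means for precision.** The plan has no figure of its own on this point. The nearest is the 70% power in 9.2, for 6 mmHg with SD 11 and 80 women. No SD is given for the six outcomes, so blood pressure stands in. Assuming a two-sided 5% level, which 9.2 does not state, and no allowance for clustering:

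power = Φ(6 / (11 × √(2/n)) − 1.96), with n per group.

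- n = 40: 6/2.460 = 2.439, power 68.4%. This is close to the stated 70%.
- n = 32 (20% lost): 6/2.750 = 2.182, power 58.8%.
- n = 33 or 34 (the middle row, 1 or 2 women recovered per group): power 60.1% or 61.4%.

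Recovering these women would gain about 1 to 3 points of power.

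**The case against.** The strongest reply is that 7.3 leaves a gap in wording and sets up no barrier. The definition uses the plural, a woman who is reached is rescheduled, every effort must be made to regain contact, 7.2 is discretionary, and 5.5 collects family contacts for this very situation. Much of that stands. In particular, a reader might infer that one missed visit removes a woman for good and that a Time 3 attempt is barred. The documents do not say so. She must also remain unreachable after at least three attempts, and no section forbids a later approach or her return.

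The safeguards still leave the gap open. Section 7.3 does not call on the family contacts. The recovery step in 5.5 starts only once attrition passes 20%, that is, more than 16 of 80 women. The plural reading leads to the same edit, because it already means that loss is assigned only after Time 3.

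Two further inferences should be resisted.

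- **Conflict with intent-to-treat.** Section 9.3 says "all subjects are included in the analysis and analyzed according to their initial randomized assignment". A disposition label in 7.3, or the three-visit completion definition in 4.4, removes no one from that set. Missing values are a separate matter.
- **Section 4.4 as the definition of retention.** No section links the two. Attendance at data collection is logged at 0, 6 and 12 months, so retention by visit can be obtained. It cannot be said from 4.4 that a month-12 attender who missed Time 2 counts as not retained.

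It is also fair to say that women who ask to leave, or who are withdrawn for pregnancy under 8.3.9, are untouched by this rule, and that 9.1 does not expect the pilot to test the main trial's hypotheses. Nothing in the documents shows which kinds of women would be unreachable.

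**Conclusion.** The point holds in a limited form. Section 7.3 equates persistent unreachability after a missed visit with study withdrawal and provides for no Time 3 attempt. Its definition and trigger, and the discretionary rule in 7.2, do not agree. Followed on the singular trigger, the rule can forgo obtainable 12-month data on six of the eight biologic primary outcomes and lower the retention rate.

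The six-of-eight count rests on the printed schedules. Section 3 speaks of change to each of Time 2 and Time 3 without listing visits by measure. The number of women affected cannot be derived. The figure of 2-4 women, or 2.5-5 points of retention, rests wholly on the assumptions that 8 of 80 are unreachable at Time 2 and that 25-50% of them can be reached at month 12. The effect on power is small. The change is worth making because the loss is avoidable, retention is itself a main product of the pilot, and the edit is cheap.

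**What to change.** - In 7.3, record unreachability at Time 2 as a missed visit. Keep the woman on the Time 3 schedule unless she asks to withdraw or is withdrawn under another protocol rule.
- Attempt contact again in the Time 3 window, including through the family contacts in 5.5.
- Assign lost to follow-up only after the Time 3 window closes. Use one wording for the definition and the trigger, and align the loss-of-contact ground in 7.2 with it.
- Report retention separately at Time 2 and Time 3, each over all women enrolled.
- Check the blood pressure rows in 1.3 and 8.1 against each other.

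The cost is a few sentences of protocol text, one more round of calls to a small number of women using contacts already collected, and a few participant records left open until month 12.

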8 STUDY ASSESSMENTS AND PROCEDURES

8.1 ENDPOINT AND OTHER NON-SAFETY ASSESSMENTS

Summary of Variables, Measurement, and Data Collection Time Points			
Variables and Measurement	0	6	12
Feasibility			
*Process evaluation checklist (bi-monthly)	--	--	--
*Screening and enrollment logs	X	X	X
*Intervention attendance	X	X	X
*Data collection attendance	X	X	X
Exit interview			X
Biological CVD Risk Factors (Primary Outcomes)			
Systolic and diastolic blood pressure	X		X
Fasting blood glucose	X		X
Fasting lipid profile	X		X
Arterial stiffness (carotid-femoral PWV)	X		X
	X	X	X
Health Behavior (Secondary Outcomes)			
Nutrition and food security	X	X	X
Physical activity questionnaire	X	X	X
Accelerometer (7 days, 24 hours/day)	X	X	X
Sleep questionnaire	X	X	X
Perceived stress	X	X	X
Coping response inventory	X	X	X
Eating self-efficacy scale	X	X	X
Exercise self-efficacy scale	X	X	X
	X	X	X
Biological Influences (Secondary Outcomes)			
Height, Weight, BMI	X	X	X
Waist Circumference	X	X	X
Hair Cortisol and Hs-CRP	X		X
Vasomotor symptoms questionnaire	X	X	X
	X	X	X
Demographic, Sociocultural, and Environmental			
Demographic questionnaire (e.g., age, education)			
Acculturation questionnaire (e.g., years in US)			
Everyday discrimination scale			
Brief resilience scale			
Health history questionnaire			
Reproductive history questionnaire			
Community food assessment			
Neighborhood risk assessment			
Physical activity resource assessment			

0 = baseline; 6 = 6-month (completion of intensive intervention and continued support); 12 = 12-month (after 6 months of maintenance on own); BMI = body mass index; Hs-CRP = high-sensitivity C-reactive protein; PWV = pulse wave velocity

*Completed by Project Manager

8.2 SAFETY ASSESSMENTS

N/A

8.3 ADVERSE EVENTS AND SERIOUS ADVERSE EVENTS

8.3.1 DEFINITION OF ADVERSE EVENTS

Definition, Expected Risks, and Potential AEs. An adverse event (AE) is any untoward medical occurrence in a participant during the clinical study, which does not necessarily have a causal relationship with the intervention. An AE may include: 1) any new signs or symptoms; 2) any new illness or disease or deterioration of an existing condition; and 3) any clinically significant abnormal laboratory assessments or clinical tests. Additionally, per UNC-CH's policy all participant deaths, protocol deviations, complaints about the research, and breaches of confidentiality are reportable AEs. A serious adverse event (SAE) is any AE that results in one or more of the following outcomes: death, a life-threatening event, inpatient hospitalization or prolongation of existing hospitalization, a persistent or significant disability/incapacity, or a serious medical event.

Identifying AEs. Potential risks identified for participants are outlined in the Protection of Human Participants section and will also be outlined in the IRB approved informed consent document. Participants will be queried about the occurrence of AEs at each visit. They will also be instructed to phone at any time during the study with an AE. The PI will work with the Safety Officer to develop a system to test whether abnormalities are equally distributed between the intervention and control groups. Data will be presented to the Safety Officer if a significant increase in abnormalities is noted. The Safety Officer will provide the PI with recommendations regarding problems that would require modification for safety reasons.

Reviewing and Reporting AEs. AEs will be reviewed by the Safety Officer and determined to be mild (no interference in usual activities); moderate (some interference in usual activities); or severe (usual activities were significantly interrupted). AEs will be categorized according to the likelihood that they are related to the study intervention. The Safety Officer will rate the assessment of attribution to the study as not related, unlikely, possible, probable, or definite to the intervention.

The PI will be responsible for ensuring that all AE and SAEs are reported to the Co-Mentors, scientific advisors, Senior RA, Safety Officer, the IRB and NIH/NIMHD within 3-7 days. An incident report will be created within 24 hours and sent by electronic email by the PI to the Co-Mentors, scientific advisors, Senior RA, Safety Officer, the IRB and NIH/NIMHD. The PI will follow-up with the participant and will prepare a report. The AEs will be reviewed every three months by the Co-Mentors, scientific advisors, the Senior RA, Safety Officer, and the PI, and a report prepared for the Human Participants Committee and the NIH/NIMHD. Process notes will be kept concerning any decisions.

Any SAE or deaths that occur during the study will be reported by telephone immediately to the Co-Mentors, scientific advisors, the Senior RA, Safety Officer, the IRB and NIH/NIMHD. An incident report will be sent by electronicmail by the PI to Co-Mentors, scientific advisors, the Senior RA, Safety Officer, the IRB and NIH/NIMHD within 24 hours. The PI will follow-up immediately with the participant to investigate and prepare a report for all members of theHuman Participants Committee and comply with all regulations regarding the reporting of SAEs. The PI will beresponsible for complying with all regulations concerning the reporting of a SAE and will prepare a full report forNIH/NIMHD. The PI will meet with the Co-Mentors, scientific advisors, and the Senior RA and seek input from the Program Officer. Process notes will be kept concerning any decisions.

8.3.2 DEFINITION OF SERIOUS ADVERSE EVENTS

See 8.3.1 above

8.3.3 CLASSIFICATION OF AN ADVERSE EVENT

See 8.3.1 above

8.3.3.1 SEVERITY OF EVENT

See 8.3.1 above

8.3.3.2 RELATIONSHIP TO STUDY INTERVENTION/EXPERIMENTAL MANIPULATION

Study Overview:

The overall goal of this project is to determine whether a multi-component intervention consisting of education and physical activity sessions, stress management, and coping skills training will decrease biologic cardiovascular risk (blood pressure, arterial stiffness, lipids, blood glucose) among perimenopausal Latinas. The DSMP outlined below will adhere to the protocol approved by The University of North Carolina at Chapel Hill (UNC-CH) Institutional Review Board (IRB) and the National Institutes of Health (NIH) and the National Institute of Minority Health and Health Disparities (NIMHD).

Monitoring Entity:

Principal Investigator (PI) and IRB. Oversight and monitoring of the conduct and progress of the study will be provided by the PI with delegation of responsibilities to designated study personnel, and the Institutional Review Board (IRB) of UNC. They will ensure all entry criteria are met prior to the initiation of the protocol and all study procedures and reporting of adverse events is performed according to the IRB-approved protocol. The PI will report adverse events to the Safety Officer, IRB, and funding agency.

Independent Safety Officer. We will appoint a Safety Officer with both clinical and intervention research expertise to provide quarterly safety monitoring throughout the conduct of the study. The Safety Officer will be independent from the study team. The Safety Officer will review the protocol, intervention components, and all data collection processes prior to study implementation. The Safety Officer will review interim data, all reports of adverse events quarterly, and, when necessary, issue recommendations to the PI regarding the continuation, modification, or termination.

Data Quality and Safety Review Plan and Monitoring:

Subject Accrual and Compliance with Inclusion/Exclusion. All data from participants screened for the study will be entered into the REDCap electronic study database. Designated research staff will collect, gather, and enter required data (written informed consent, Health Insurance Portability and Accountability Act (HIPAA) authorization, medical history and demographics) onto study data forms. Screened patients who do not meet study eligibility will have specific screening data entered into the study database. The collected data will be helpful in examining the patient population and feasibility of enrollment criteria and will include gender, age, race and reason for exclusion. All dates will be shifted and other Personal Health Information (PHI) will be removed from the study database upon study completion.

Participant Compliance to the Intervention. Data on compliance to the intervention will be collected weekly by the senior RA and reviewed quarterly by the Co-Mentors, scientific advisors, the Senior RA, Safety Officer, and PI. Compliance on the part of participants will be evaluated by attendance and process evaluation as outlined in the study. If intervention attendance drops below 80%, participants who have stopped coming will be called to ask for feedback. Using information gained from these phone interviews, the PI will schedule a meeting with the Co-mentors, scientific advisors, and the Safety Officer to discuss methods for improving compliance.

Study Visits and Data Collection. The PI and [name] (Study Statistician) will oversee and train the senior RA to establish a system to ensure the verification of source data compliance. The source data will include original records necessary for the reconstruction and evaluation of the clinical trial. It will be clear who documented the data, documentation will be readable, signatures identifiable, concurrent, original copy, accurate and consistent, long-lasting and durable, available and accessible, complete, consistent, credible, and corroborated. All data will be first checked by two separate Research Assistants (RAs) at different times. Data entry and monitoring will be completed in REDCap, our Research Electronic Data Capture System. The PI has been trained in REDCap and has used it in previous studies and REDCap is supported by UNC-CH. [name] will oversee the development of the REDCap database and train RAs how to compare data entry against source data and make corrections as needed. [name] will develop a data dictionary to support accurate data entry between RAs and a data log book will be created to establish an audit trail for compliance.

Ongoing quality control procedures will be implemented for data collection, storage and processing. The senior RA will conduct monthly monitoring of the study database and generate

a report for the PI to review at team meetings. Standing agenda items for these meetings will include participant recruitment and retention, AEs, SAEs, protocol deviations, data integrity and overall study conduct.

8.3.3.3 EXPECTEDNESS

N/A

8.3.4 TIME PERIOD AND FREQUENCY FOR EVENT ASSESSMENT AND FOLLOW-UP

The frequency of event assessment and follow-up for this study is summarized in the table below.

Frequency of Data Review		
Data Type	Frequency of Review	Reviewer
Subject accrual (including compliance with enrollment criteria)	Monthly	Co-Mentors, scientific advisors, the project coordinator, and Safety Officer
Status of enrolled subjects as of date of reporting	Quarterly	Co-Mentors, scientific advisors, the senior RA, and Safety Officer
Adherence data regarding study visits and intervention	Quarterly	Co-Mentors, scientific advisors, the senior RA, and Safety Officer
AEs and rates	Quarterly	Co-Mentors, scientific advisors, the senior RA, and Safety Officer

Safety Review Plan. Study progress and safety will be reviewed monthly. The PI will provide progress reports, including patient recruitment, attrition, and AEs to the Co-Mentors, scientific advisors, the senior RA, and Safety Officer following each of the monthly reviews. An Annual Report will be compiled including 1) a list and summary of AEs; 2) whether AE rates are consistent with pre-study assumptions; 3) reason for dropouts from the study; 4) whether all participants met enrollment criteria; 5) whether continuation of the study is justified on the basis that additional data are needed to accomplish the stated aims of the study; and 6) conditions whereby the study might be terminated prematurely. The Annual Report will be sent to the Co-Mentors, scientific advisors, the senior RA, and Safety Officer and forwarded to the IRB and NIH/NIMHD. The IRB will review progress of this study on an annual basis. The PI will also send copies of signed recommendations and comments from the Safety Officer to the NIMHD Program Officer within 1 month of each monitoring review.

Interim Analysis. The senior RA will generate semi-annual qualitative interim analysis reports on data obtained during phone call and returned end-of-study surveys to understand issues related to the uptake, usability, and adoption of this platform among this population. We will evaluate the screening and enrollment procedures, barriers to participation and retention, acceptability, technology problems encountered if any, and user feedback from the participants.

The information gained from this structured process will be used to both guide the refinement of the current protocol and to inform the design of a larger efficacy trial. **Stopping Rules**. There are no planned stopping rules for this study. **Protocol Modifications**. Modifications will not be undertaken without notification of the IRB, Safety Officer, and NIMHD Program Officer.

